8.3 Pregnancy Outcomes

The number and percentage of pregnancy outcomes (full term live birth [≥ 37 0/7 weeks], premature live birth [< 37 0/7 weeks], stillbirth/intrauterine fetal demise [≥ 20 0/7 weeks], and spontaneous abortion [< 20 0/7 weeks]) and the exact binomial confidence intervals for those proportions will be summarized by study arm and overall for each of the three cohorts, and by study arm and overall for the three cohorts combined. This analysis will include all participants in the analysis set who had an obtainable pregnancy outcome. If a participant was found to have a non-singleton pregnancy after enrollment then each outcome from that pregnancy will be included in this analysis.

A secondary analysis will be conducted by repeating the pregnancy outcome summaries for only participants who received study product (i.e., the participants in the Product Exposure Set).

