2.1 General Design Considerations

The following is a summary of Protocol Version 2.0

Short Title:	DELIVER: A Phase 3b Safety Study of the Dapivirine Ring and PrEP in Pregnant Women
IND Sponsor:	DAIDS
Funders:	Division of AIDS, NIAID, NIMH, NICHD, US NIH
Protocol Chair:	[name], MPH [name], MMed
Protocol Co-Chair:	[name], FCPaeds
Sample Size:	Approximately 550 women and their infants
Study Population:	Healthy, HIV-uninfected pregnant females, 18-40 (inclusive) years old, with an uncomplicated singleton pregnancy who are willing to be randomized to study product, and their infants
Study Sites:	MTN-042 site(s) selected by the MTN Executive Committee
Study Hypotheses:	
 • Daily use of Truvada oral tablet and dapivirine (DPV) vaginal matrix ring (25 mg) inserted once every 4 weeks will both be generally safe and well-tolerated by the participants and their fetuses/infants. • Participants who use Truvada oral tablet daily and insert the DPV vaginal matrix ring (25 mg) once every 4 weeks will experience similar distributions of pregnancy outcomes to the general population.
Study Design:	Phase 3b, two-arm, open label, multi-site, randomized (2:1) trial (DPV vaginal ring [VR], Truvada oral tablet), with onset of dosing period to occur within the following gestational age (GA) ranges: 
Cohort 1: 36 0/7 weeks – 37 6/7 weeks 150 women Cohort 2: 30 0/7 weeks – 35 6/7 weeks 150 women Cohort 3: 12 0/7 weeks – 29 6/7 weeks 150 women

Study Duration:	The total duration of study participation for each participant will vary depending on gestational age at time of enrollment and length of pregnancy prior to pregnancy outcome, and will range from approximately 12 weeks or less for Cohort 1 to approximately 36 weeks or less for Cohort 3. Participants who

become infected with HIV will continue in study follow-up with a modified study visit/procedure schedule for a minimum of twelve months. Also, infants born to MTN-042 participants will be followed for approximately 52 weeks (i.e., one year)

Study Products:

- Silicone elastomer matrix VR containing 25 mg of DPV
- Oral tablets (Truvada) containing 200 mg emtricitabine/300 mg tenofovir disoproxil fumarate (FTC/TDF)

Study Regimen:

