2.2 Study Objectives and Endpoints

Primary Objectives:

Maternal and Infant Safety: To describe the maternal and infant safety profile associated with

study product exposure during pregnancy

Pregnancy Outcomes: To describe the pregnancy outcomes associated with study product exposure during pregnancy

Primary Endpoints:

-

Maternal Safety (composite)

- All serious adverse events, including maternal deaths
- All Grade 3 or higher adverse events (AE) as defined by the Division of AIDS (DAIDS) Table for Grading the Severity of Adult and Pediatric Adverse Events, Corrected Version 2.1, July 2017 and/or Addendum 1 (Female Genital Grading Table for Use in Microbicide Studies [Dated November 2007])

Infant Safety (composite)

- All serious adverse events, including infant deaths and congenital anomalies
- All Grade 3 or higher AEs as defined by the Division of AIDS (DAIDS) Table for Grading the Severity of Adult and Pediatric Adverse Events, Corrected Version 2.1, July 2017

Pregnancy Outcomes

- Frequency of the following pregnancy outcomes:
 - Full term live birth (≥ 37 0/7 weeks)
 - Premature live birth (< 37 0/7 weeks)
 - Pregnancy loss (≥ 20 0/7 weeks)
 - Pregnancy loss (< 20 0/7 weeks)

Secondary Objectives:

Pregnancy Complications: To describe pregnancy complications associated with study product exposure during pregnancy

Infant Drug Levels: To describe infant levels of study drugs associated with study product exposure during pregnancy

Adherence: To characterize adherence to open label use of the DPV VR (25 mg) and oral Truvada in pregnant women

Acceptability: To characterize acceptability of open label use of the DPV VR (25 mg) and oral Truvada in pregnant women

Secondary Endpoints:

Pregnancy Complications

- Frequency of the following pregnancy complications:
 - Hypertensive disorders of pregnancy
 - Chorioamnionitis
 - Puerperal sepsis and endometritis
 - Antepartum, intrapartum and postpartum hemorrhage
 - Preterm premature rupture of membranes (PROM)
 - Fever of unclear etiology

Infant Drug Levels

- Infant blood tenofovir diphosphate (TFV-DP) and emtricitabine triphosphate (FTCTP) concentrations
- Infant plasma DPV concentrations

Adherence

- Maternal blood TFV-DP and FTC-TP concentrations
- Maternal plasma DPV concentrations
- Participant report of frequency of study product use (e.g., missed doses for oral Truvada and VR removal/expulsions [voluntary and involuntary] and duration without VR in vagina)

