Based on pregnancy outcome data from previous studies, we expect certain pregnancy outcomes such as premature live birth and pregnancy loss \geq 20 weeks to occur at a low frequency (5% and 2-3%, respectively). Among all women who became pregnant in MTN-003 (VOICE) and MTN-020 (ASPIRE), pregnancy loss $<$ 20 weeks was between 19-22%. Given the enrollment criteria for this study, it is expected that the frequency of pregnancy loss $<$ 20 weeks will be lower in enrolled MTN-042 participants. As such, the probability and confidence interval estimates presented in Table 1 and Table 2 also apply to estimates of the frequency of pregnancy outcomes. For example, if there was one stillbirth among the 100 participants in Cohort 1 receiving the VR regimen, the stillbirth frequency would be 1.00% and the 95% exact 2-sided confidence interval would be (0.03, 5.45).

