8. PRIMARY ENDPOINTS

An intent to treat analysis will be performed to summarize the frequency of primary endpoints (maternal safety, infant safety and pregnancy outcome) by study arm (ITT Analysis Set). An additional analysis will be conducted including only visits in which a participant has been exposed to the study product (Product Exposure Set). Analyses will be conducted separately for each of the three cohorts (including an exploratory analysis that splits Cohort 3 based on gestational age as described in Section 5), with a final aggregate analysis that will include all enrolled participants from each of the three cohorts. The number and the percentages of participants experiencing each primary endpoint will be tabulated by study arm. Each participant will contribute once in each category (i.e., only for highest severity AE for each

participant) for the calculation of event rates. Exact binomial confidence intervals will be calculated for each primary endpoint. Primary endpoint event rates will be compared to baseline estimates from MTN-042B by checking whether the baseline estimates are included in the exact binomial confidence intervals (this will not be included as part of the CSR). A secondary analysis will be performed to summarize the total number of primary and secondary safety endpoints reported per participant by study arm.

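### Section 8.3 puts women who cannot have a loss before 20 weeks into that outcome's percentage and exact interval, so the Cohort 3 and pooled figures are diluted and too precise

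*SAP*

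**What the plan says.** Section 8.3 tabulates four outcomes: full-term live birth, premature live birth, stillbirth or fetal demise from 20 0/7 weeks, and spontaneous abortion before 20 0/7 weeks. On the denominator it says: "This analysis will include all participants in the analysis set who had an obtainable pregnancy outcome". The percentages "and the exact binomial confidence intervals for those proportions will be summarized by study arm and overall for each of the three cohorts", and again for the cohorts combined. Nothing restricts the denominator by gestational age at enrollment.

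Section 2.1 gives the enrollment windows. Cohort 1 enters from 36 0/7 up to 37 6/7 weeks and Cohort 2 from 30 0/7 up to 35 6/7. The entry for the earliest cohort reads: "Cohort 3: 12 0/7 weeks – 29 6/7 weeks 150 women".

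The Cohort 3 size printed there conflicts with the rest of the SAP. The regimen text in 2.1 and Table 1 give 200 ring and 50 tablet, which also fits the total of 550 (150 + 150 + 250). I use 200 and 50.

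Section 2.6 expects fewer losses before 20 weeks because of the enrollment criteria, yet says that "the probability and confidence interval estimates presented in Table 1 and Table 2 also apply to estimates of the frequency of pregnancy outcomes". Those tables use full cohort and full arm sizes.

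Section 8, whose primary endpoints include pregnancy outcome, says: "Analyses will be conducted separately for each of the three cohorts (including an exploratory analysis that splits Cohort 3 based on gestational age". Sections 8.1 and 8.2 repeat this split. Section 8.3 does not, and Section 5 confines the split to analyses for which the SAP specifies it.

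**The concern.** An exact binomial interval treats every person in the denominator as someone who could have had the event. For loss before 20 weeks that is false for all of Cohort 1, all of Cohort 2, and every Cohort 3 woman enrolled at 20 0/7 weeks or later. Each such woman adds a certain non-event. The percentage falls and the upper limit shrinks, with no information gained about early loss.

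Pregnancy outcome is a primary endpoint and the subject of a primary hypothesis. The usual question about a rare adverse outcome is how large a risk the data exclude, and the planned intervals answer it too favorably for early loss. A milder form affects premature birth, because Cohort 1 women enrolled at 37 weeks have already passed the threshold.

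**Working it through.** **Inputs.** Planned ring-arm sizes (Section 2.6): 100 in each of Cohorts 1 and 2, 200 in Cohort 3, 400 in all. Tablet: 50 per cohort, 150 in all. Intervals are exact, two-sided, 95%. Every woman is taken to have an obtainable outcome.

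**Formula.** With zero events among n women, the exact upper limit is U = 1 − 0.025^(1/n).

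**The plan's own figures.** n = 400 gives 0.92%, n = 200 gives 1.83%, n = 150 gives 2.43%, n = 100 gives 3.62% and n = 50 gives 7.11%. All match Table 2. The Section 2.6 example of one stillbirth in 100 women, 1.00% (0.03, 5.45), also reproduces.

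**Who can have a loss before 20 weeks.** Cohort 1 (from 36 0/7): nobody. Cohort 2 (from 30 0/7): nobody. Cohort 3 (12 0/7 to 29 6/7): only women enrolled at 12 0/7 to 19 6/7. Their number is not given, so I assume a range. An even spread over completed weeks 12 to 29 puts 8 of 18 weeks below 20, and 200 × 8/18 ≈ 89.

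**Ring arm, zero losses before 20 weeks**

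| Denominator | n | Upper limit |
|---|---|---|
| Pooled, as planned | 400 | 0.92% |
| Cohort 3, as planned | 200 | 1.83% |
| Cohort 1 or 2, as planned (nobody at risk) | 100 | 3.62% |
| At risk, 75% of Cohort 3 (assumed) | 150 | 2.43% |
| At risk, 50% (assumed) | 100 | 3.62% |
| At risk, even spread (assumed) | 89 | 4.06% |
| At risk, 25% (assumed) | 50 | 7.11% |

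The pooled percentage is diluted by 400/150 ≈ 2.7 to 400/50 = 8 times, and by 400/89 ≈ 4.5 at even spread. The Cohort 3 percentage is diluted by 200/150 ≈ 1.3 to 200/50 = 4 times.

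**Ring arm, two losses.** Pooled: 2/400 = 0.50% (0.06, 1.79). Cohort 3: 2/200 = 1.00% (0.12, 3.57). At risk, even spread: 2/89 = 2.25% (0.27, 7.88).

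**Tablet arm, zero losses.** Pooled as planned, n = 150: 2.43%. At risk, even spread, 50 × 8/18 ≈ 22: 15.44%.

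**Premature birth.** Only Cohort 1 women enrolled at 37 weeks are affected; their number is not given either. If 25%, 50% or 75% of the 100 Cohort 1 ring women enrolled at 37 weeks, then 75, 50 or 25 are at risk. The zero-event upper limit is 4.80%, 7.11% or 13.72%, against 3.62% as planned. Pooled, at the 5% that Section 2.6 expects, 20/400 = 5.00% (3.08, 7.62) becomes 20/350 = 5.71% (3.53, 8.69) if half enrolled at 37 weeks. At 25% and 75% it becomes 20/375 = 5.33% and 20/325 = 6.15%.

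**The case against.** The strongest reply is that Section 8 already sets the Cohort 3 split for all primary endpoints, and its 12 0/7 to 19 6/7 group is exactly the at-risk group for early loss. A reader might infer that the plan has no such breakdown. The text does not support that: 8.3 is silent on a rule given one level up. The silence still leaves doubt, since 8.1 and 8.2 do repeat the rule and Section 5 requires the split to be specified. The split is also only exploratory and changes neither the main Cohort 3 figure nor the pooled one.

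Second, the endpoint is a descriptive distribution. As shares of outcomes among enrolled women, the percentages are arithmetically correct, and the cohort columns let a careful reader discount Cohorts 1 and 2. That stands, and it is why the table should stay. It does not justify reading an exact interval over women not at risk as a limit on risk.

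Third, a reader might infer that the planned check against MTN-042B, or the contrast between arms, would be misled. The documents give little support for this. Section 3.2 says MTN-042B by design misses early losses, the check is outside the clinical study report, and no test between arms is planned for pregnancy outcomes. Dilution does differ by arm, since Cohort 3 is 200 of 400 ring women and 50 of 150 tablet women, but it feeds no planned comparison.

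Fourth, at-risk denominators do not remove late entry: a woman enrolled at 19 6/7 counts the same as one enrolled at 12 0/7. True, but she could still have the event.

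Fifth, 8.3 does not say which gestational age classifies the outcome, and Section 6.2 mentions a best estimate at delivery on the Pregnancy Outcome CRF. If that estimate is used, a woman enrolled at 37 0/7 could be classified as premature. So impossible is too strong for premature birth unless the source is fixed.

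**Conclusion.** The point holds for loss before 20 weeks. The planned Cohort 3 and pooled percentages are diluted and their upper limits too small, and the Cohort 1 and 2 intervals have no meaning for this outcome. With 50 to 150 of the 200 Cohort 3 ring women at risk, the zero-event limit is 7.11% to 2.43% (4.06% at even spread), against the planned 0.92% and 1.83%. The direction follows from the enrollment ranges alone, provided some Cohort 3 women enrolled at 20 weeks or later. The size rests on assumed at-risk counts.

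For premature birth the effect is material in the Cohort 1 column (3.62% to 7.11% if half enrolled at 37 weeks) and small in the pooled column (5.00% to about 5.7%). A claim that pooled prematurity is seriously distorted is not supported.

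Separately, Section 2.2 speaks of pregnancy loss, while 8.3 names only stillbirth or fetal demise and spontaneous abortion. An induced termination would then have no row in 8.3 as worded. A reader might infer that terminations must count as losses. That is one reading of 2.2, and the document does not settle it. It needs only to be stated.

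**What to change.** - Keep the outcome distribution table over all women with an obtainable outcome.
- For loss before 20 weeks, base the percentage and exact interval on women with an obtainable outcome who enrolled before 20 0/7 weeks, in the Cohort 3 and pooled columns. Print the at-risk n, and show not applicable for Cohorts 1 and 2.
- State the Section 5 split of Cohort 3 in 8.3, as 8.1 and 8.2 do.
- In Section 2.6, limit the statement that Tables 1 and 2 apply, so that for this outcome it refers to the at-risk n.
- Lesser: for premature birth, use women enrolled before 37 0/7 weeks, and take gestational age at enrollment and at outcome from the same source.
- Reconcile the loss categories in 2.2 and 8.3 so that every outcome in the denominator falls in a row.

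The cost is SAP wording and table shells. Section 3.2 says gestational age at enrollment is already on the Pregnancy Assessment CRF. The downside is wider intervals, which show what the data can support.

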An alternative way of describing the statistical properties of the study design is in terms of the 95% confidence interval for the “true” rate based on the observed data. The table below shows the exact 2-sided 95% confidence intervals for the probability of an event based on a particular observed rate. For example, if none of the 400 participants receiving the VR regimen experience a safety event, the 95% exact 2-sided upper confidence bound for the true rate of such events in a particular arm of the study is 0.92%.

Table 2. Confidence intervals for endpoint rate (proportion of participants with endpoint) given number of endpoints (rows) in with number of participants (columns)

Number of events	Number of participants ^a				
	n=50	n=100	n=150	n=200	n=400
0	0.00, 7.11	0.00, 3.62	0.00, 2.43	0.00, 1.83	0.00, 0.92
1	0.05, 10.65	0.03, 5.45	0.00, 3.66	0.01, 2.75	0.00, 1.38
2	0.49, 13.71	0.24, 7.04	0.16, 4.73	0.12, 3.57	0.06, 1.79
3	1.25, 16.55	0.62, 8.52	0.41, 5.73	0.31, 4.32	0.15, 2.18
4	2.22, 19.23	1.10, 9.93	0.73, 6.69	0.55, 5.04	0.27, 2.54
5	3.33, 21.81	1.64, 11.28	1.09, 7.61	0.82, 5.74	0.41, 2.89

Number of events	Number of participants ^a				
	n=50	n=100	n=150	n=200	n=400
6	4.53, 24.31	2.23, 12.60	1.48, 8.50	1.11, 6.42	0.55, 3.24
8	7.17, 29.11	3.52, 15.16	2.33, 10.24	1.74, 7.73	0.87, 3.90
10	10.03, 33.72	4.90, 17.62	3.24, 11.92	2.42, 9.00	1.21, 4.55
12	13.06, 38.17	6.36, 20.02	4.20, 13.56	3.14, 10.25	1.56, 5.18
15	17.86, 44.61	8.65, 23.53	5.71, 15.96	4.26, 12.07	2.11, 6.11
20	26.41, 54.82	12.67, 29.18	8.34, 19.84	6.22, 15.02	3.08, 7.62
30	45.18, 73.59	21.24, 39.98	13.92, 27.30	10.35, 20.72	5.12, 10.53

^aSample sizes in the table based on the proposed cohort size and study design.

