5. GENERAL ANALYSIS METHODS

When the use of descriptive statistics to assess group characteristics or differences is described, the following methods will be used: for categorical variables, the number and percent in each category; for continuous variables, the mean, median, standard deviation, quartiles, and range (minimum, maximum).

Descriptions of tabular summaries that are “by study arm and overall” indicate that the table should have columns summarizing each arm as well as a column summarizing the combined arms.

Tabular summaries by visit do not include interim visits, unless otherwise noted. Results from all visits (including interim visits) will be included in listings.

[figure not shown]
In addition to separate analyses/summaries for each of the three cohorts, an exploratory analysis will split Cohort 3 participants into two groups based on gestational age (20 0/7 weeks through 29 6/7 weeks and 12 0/7 weeks through 19 6/7 weeks) as collected on the Pregnancy Assessment CRF. These ages were originally going to be two separate cohorts in Protocol Version 1.0 before being combined into one cohort in Protocol Version 2.0. These exploratory analyses splitting Cohort 3 will be done only for certain analyses, as specified in this document.

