9. SECONDARY ENDPOINTS

9.1 Pregnancy Complications

Pregnancy complications will be summarized in tables by study arm and overall for each of the three cohorts, and by study arm and overall for the three cohorts combined. This analysis will include all participants in the analysis set who had an obtainable pregnancy outcome.

The summaries of complications will include the following complications, gathered on the Pregnancy Outcome CRF:

- any hypertensive disorders of pregnancy, and the different individual types of hypertensive disorders:
 - chronic
 - gestational
 - pre-eclampsia without severe features
 - pre-eclampsia with severe features
 - eclampsia
 - not specified
- chorioamnionitis
- either of puerperal sepsis or endometritis (combination of the puerperal sepsis and endometritis items), and summaries of both individually:
 - puerperal sepsis
 - endometritis
- either of peripartum and postpartum hemorrhage (Cohort 1 only)
- either of antepartum, intrapartum, or postpartum hemorrhage (Cohorts 2 and 3 only), and summaries of each type of hemorrhage individually:
 - peripartum hemorrhage (Cohort 1 only)
 - antepartum hemorrhage (Cohorts 2 and 3 only)
 - intrapartum hemorrhage (Cohorts 2 and 3 only)
 - postpartum hemorrhage
- preterm premature rupture of membranes (PROM) (the preterm premature rupture of membranes (PPROM) item)
- fever of unclear etiology
- other

The table will include a footnote listing the responses to "If 'Other', specify" for complications categorized as other. The number and percentage of participants, and the exact binomial confidence intervals for those proportions, with these complications will be summarized. The denominator will be the number of participants in the analysis set with a pregnancy outcome.

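### Loss before 20 weeks is divided mostly by women enrolled too late to have it, and the precision claimed from Tables 1 and 2 does not hold for that outcome

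*SAP*

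**What the plan says.** Section 8.3 tabulates full-term live birth, premature live birth (before 37 0/7), stillbirth (from 20 0/7) and spontaneous abortion (before 20 0/7) with exact binomial intervals. The denominator is the same for each: "This analysis will include all participants in the analysis set who had an obtainable pregnancy outcome". Results "will be summarized by study arm and overall for each of the three cohorts, and by study arm and overall for the three cohorts combined". Gestational age at enrolment plays no part. Section 9.1 treats complications, including preterm PROM, in the same way: "The denominator will be the number of participants in the analysis set with a pregnancy outcome".

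Section 2.1 sets the entry windows. The latest is "Cohort 1: 36 0/7 weeks – 37 6/7 weeks 150 women"; Cohort 2 enters at 30 to 35 completed weeks and Cohort 3 at 12 to 29.

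On precision, section 2.6 states that "the probability and confidence interval estimates presented in Table 1 and Table 2 also apply to estimates of the frequency of pregnancy outcomes". It expects early loss to be less frequent than in previous studies because of the entry criteria, but does not say that most participants cannot have one.

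The opening of section 8 counts pregnancy outcome among the primary endpoints and plans analyses by cohort, "including an exploratory analysis that splits Cohort 3 based on gestational age as described in Section 5". Section 5 defines the two groups as "20 0/7 weeks through 29 6/7 weeks and 12 0/7 weeks through 19 6/7 weeks" and confines the split to analyses for which the SAP specifies it. Sections 8.1 and 8.2 repeat the split; 8.3 does not.

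**The concern.** A proportion describes risk only if the people counted could have had the event. A woman randomized at 36 weeks is already past the period in which a loss before 20 weeks is possible. Counting her as a non-event lowers the percentage and narrows the interval without adding information.

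For early loss this affects every woman in Cohorts 1 and 2 and the later-enrolled part of Cohort 3. The pooled row, with the largest n and the tightest interval, is the most diluted. A reader could take 0% with a narrow interval in Cohort 1 as evidence of safety when the result was fixed by design. There is no external check either: section 3.2 says that the background chart review would not capture early losses.

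The 20-week split would isolate the women at risk of early loss. A programmer working from 8.3 alone would leave it out.

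**Working it through.** **Inputs.** Planned ring:tablet numbers are 100:50 in each of Cohorts 1 and 2, 200:50 in Cohort 3, and 400:150 pooled (2.1 study regimen; Table 1 and its footnote). The design summary in 2.1 lists 150 women for Cohort 3, which does not fit the total of about 550; 250 is used here, as in Table 1. Table 2 gives "exact 2-sided 95% confidence intervals for the probability of an event based on a particular observed rate". The SAP gives no distribution of gestational age at enrolment, so at-risk counts within Cohort 3 are assumptions.

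**Reproducing the plan.** With zero events the exact upper limit is 1 − 0.025^(1/n). For n = 400 this gives 0.92%, and for n = 150 it gives 2.43%, as printed. Of the 65 cells in Table 2, 64 agree within 0.01. The exception, the lower limit for 1/150 (printed 0.00, computed 0.02), does not matter here.

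**Who is at risk of loss before 20 weeks.**
- Cohorts 1 and 2: none of 200 ring and none of 100 tablet women.
- Cohort 3: only women enrolled before 20 0/7, so at most 200 ring and 50 tablet.
- Even enrolment over the 18-week Cohort 3 window (assumed): 8/18 = 44%, or 0.444 × 200 ≈ 89 ring and 0.444 × 50 ≈ 22 tablet.

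**Dilution.** Pooled percentage = at-risk percentage × m/N, where m is the number at risk and N the number counted.
- Ring: at most 200/400 = 1/2; under even enrolment 89/400, a factor of about 4.5.
- Tablet: at most 50/150 = 1/3; under even enrolment 22/150, a factor of about 6.8.

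**Zero-event upper limits for loss before 20 weeks.**

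| Arm | Table 2, pooled n | All Cohort 3 at risk | Even enrolment | Small at-risk group |
|---|---|---|---|---|
| Ring | 0.92% (400) | 1.83% (200) | 4.06% (89) | 7.11% (50) |
| Tablet | 2.43% (150) | 7.11% (50) | 15.44% (22) | 30.85% (10) |

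Intermediate ring values are 2.43% for 150 at risk and 3.62% for 100. Cohort 1 and 2 cells would print 0% with upper limits of 3.62% (n = 100) and 7.11% (n = 50), although nobody in them is at risk.

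**With events.** Five losses in the ring arm would print as 5/400 = 1.25% (0.41 to 2.89) pooled and 5/200 = 2.50% (0.82 to 5.74) for Cohort 3. Among 89 at risk they are 5/89 = 5.6% (1.85 to 12.63).

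**Table 1.** At a true rate of 1%, the chance of no event among 400 is 0.99^400 = 1.80%, as printed. Among 89 at risk it is 0.99^89 = 40.9%.

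**Premature live birth.** All Cohort 2 and 3 women are at risk. Only Cohort 1 women enrolled at 37 0/7 or later are not, so at most 100/400 = 25% (ring) or 50/150 = 33% (tablet) of the pooled denominator is affected. In the worst case the pooled ring zero-event limit is 1.22% (n = 300) against 0.92%, and 15 events give 15/300 = 5.00% (2.83 to 8.11) against 15/400 = 3.75% (2.11 to 6.11). Within Cohort 1, if half the 100 ring women enrolled at 36 weeks, two events give 2/50 = 4.0% (0.49 to 13.71) against 2/100 = 2.0% (0.24 to 7.04). The same counts apply to preterm PROM if preterm means before 37 0/7.

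**The case against.** The best defence is that the common denominator is deliberate. The endpoint is the frequency of a set of outcomes and the hypothesis concerns their distribution. One denominator makes the four categories add up, and the exact interval is valid for the proportion of enrolled women. This stands: it is why at-risk rows should sit beside the distribution and not replace it, and why it would be too strong to call the tabulated percentage simply biased.

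A reader might infer that an early-loss signal would be averaged away altogether. The SAP does not support that. Cohort 3 is tabulated separately, so Cohorts 1 and 2 dilute only the pooled row, and the opening of section 8 already promises the split at 20 weeks. What remains is that 8.3 omits the split where 8.1 and 8.2 repeat it, that it is only exploratory, and that the pooled row stays diluted.

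A reader might also infer that the stated precision is lost for premature birth as well. It is reduced, not absent: the Cohort 2 and 3 figures are unaffected.

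Two cautions apply to the remedy. First, being not at risk is a matter of enrolment dating. Section 6.2 shows that a best estimate at delivery may also exist, and fixes the enrolment-based derivation only for its own summary. If 8.3 used the delivery estimate, a woman dated at 37 0/7 on entry could be recorded as a premature birth. Second, women at risk of early loss have unequal time at risk, from one day (enrolled at 19 6/7) to eight weeks (enrolled at 12 0/7), so the at-risk percentage is not a single underlying risk.

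Finally, the analyses are descriptive and no test depends on this. The worked example in 2.6, one stillbirth among 100 Cohort 1 ring women, is correct because all of them are at risk.

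**Conclusion.** The point holds for loss before 20 weeks. That the pooled percentage is at most one half (ring) or one third (tablet) of the at-risk percentage needs only the planned arm sizes and entry windows. So does the finding that the pooled zero-event limits should be at least about twice (ring, 1.83/0.92) and about three times (tablet, 7.11/2.43) those in Table 2. The larger figures, 4.06% and 15.4%, rest on even enrolment across the Cohort 3 window, which the SAP neither states nor rules out. The statement in 2.6 is wrong for this outcome as worded and right for stillbirth.

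For premature live birth and preterm PROM the effect is secondary and confined to Cohort 1 and the pooled row. Section 8.3 also needs to be reconciled with the opening of section 8 on the Cohort 3 split.

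**What to change.** - **8.3:** Keep the four-category distribution. Add an at-risk row, with its n and exact interval, for loss before 20 weeks (women below 20 0/7 at enrolment) and for premature live birth (women below 37 0/7 at enrolment).
- **8.3:** For loss before 20 weeks, mark the Cohort 1, Cohort 2 and Cohort 3 20-to-29-week cells as not at risk and print no interval.
- **8.3:** Name the Cohort 3 split already promised in section 8.
- **8.3:** State which source of gestational age classifies the outcome. List any event in a woman flagged as not at risk; do not drop it.
- **9.1:** Add the corresponding at-risk row for preterm PROM.
- **2.6:** Limit the statement about Tables 1 and 2 to outcomes for which every woman counted is at risk. Give the wider limits for loss before 20 weeks over a range of at-risk n, for example 50 to 200 ring and 10 to 50 tablet.

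Gestational age at enrolment is already on the Pregnancy Assessment CRF, so no new data are needed. The cost is a flag in the analysis data, a few extra rows, and a less favourable stated precision for early loss.
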